#### Primary Outcome

-Proportion of patients transfused at least 1 unit of packed red blood cells during hospital admission

#### Secondary Outcomes

-Mean number of units transfused per patient

-Calculated blood loss

-Incidence of symptomatic VTE diagnosed within 6 months of surgery

- Wound complications diagnosed within 6 months of surgery
- MI diagnosed within 6 months of surgery
- CVA diagnosed within 6 months of surgery
- All-cause mortality at 6 months

## Safety Monitoring

## Statistical Considerations

### Randomization and Blinding

Subjects will be randomized into one of two study groups: TXA administration (treatment) or placebo (control). Subjects will be assigned to either the treatment group or control group using a pre-generated blocked randomization design. The randomization schedule will be developed by the study statistician and will be provided to Research pharmacy personnel who will make the study group assignment. Medications

will then be delivered to the emergency department in packaging that does not delineate whether it contains placebo or tranexamic acid. Thus, the patient, treating surgeon, emergency department physician, residents, hospitalist group, anesthesiologist, and data collectors will remain blinded to the treatment assignment.

### Analysis

The primary outcome will be the proportion of patients transfused at least 1 unit of packed red blood cells during hospital admission. Secondary outcomes will include mean number of units transfused per patient, calculated blood loss, and incidence of adverse events at six months including: VTE, MI, CVA, wound complications, and all-cause mortality as previously defined. The cohort of patients treated with early administration of TXA in the ED will be compared to a control group who were not treated with TXA at any point. All outcomes will be reported descriptively using appropriate summary statistics, including 95% confidence intervals, where appropriate. Baseline variables, including fracture type, surgical procedure, presenting hemoglobin, history of coronary artery disease, American Society of Anesthesiologists (ASA) score, length of surgery, length of anesthesia and type of anesthesia will be summarized overall and separately by study group; because this is a prospective, randomized trial, no formal between-group comparisons of baseline covariates will be performed. Adverse events as well as the primary and secondary outcomes occurring during the hospital stay and up to six months following surgery will be evaluated using chi-square tests and logistic regression (for categorical variables) if complete follow-up is obtained for the study subjects. If follow-up varies because of subject withdrawal or lack of response at 6 months, these outcomes will be estimated and evaluated using survivorship methods such as Kaplan-Meier estimation and Cox proportional hazards regression. Two-sample t-tests will be used to compare continuous variables between the study groups. All statistical tests will be two-sided and the threshold of statistical significance will be set at  $\alpha = 0.05$ .

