**Initial Patient Encounter**

The Orthopedic Trauma Service (OTS) in the emergency department will perform a history and physical exam. Hip radiographs will be obtained to evaluate fracture type and indicated operative procedure. If study criteria are met, informed consent will be obtained either from the patient or legally authorized representative. After consent is obtained, treatment will be initiated in the emergency room with study medication obtained by ED pharmacy.

TXA will be administered intravenously via bolus dose of 1g over ten minutes and an additional 1g over the subsequent 8 hours, in accordance with a previously studied protocol utilized in the CRASH-2 trial [2, 3]. Patients in the control group will receive a placebo medication in the ED. Neither group will receive perioperative bolus dosing of TXA.

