#### Clinical Follow-up

Patient follow-up and disposition will be at the discretion of the treating surgeon. For the purposes of this study, patients will be followed for a period of six months from the day of surgery. At the time of follow-up, patients will be assessed for the incidence of complication including VTE, MI, CVA, wound complication, and all-cause mortality. If patients are not able to return to clinic, they (or their legally authorized representative) will be contacted by phone.

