### Sample Size

In a prospective randomized, controlled trial conducted in Denmark evaluating a similar outcome in the same patient population, there was a transfusion rate of 84.6% in the control group, who never received

TXA [9]. However, a retrospective evaluation of the transfusion rate for the population of interest at our institution in 2014 with standard transfusion thresholds as reflected in the above described protocol was 50%. Utilizing this transfusion rate, the sample size was calculated to be able to detect a difference of 50% versus 25% (a reduction of risk by 1/2) between the control group and treatment group, respectively. A sample of 58 subjects per study group (116 in total) will provide 80% power to detect a difference in the proportion of patients receiving blood transfusion of 50% versus 25% ( $\alpha=0.05$ , two-sided test) [10]. We will assume an attrition rate of at least 15%, thus the target sample size will be 78 patients per group, 156 in total.

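### The compared cohorts are described by TXA receipt, and nothing in the plan says that randomised patients are analysed in their assigned group

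*Combined protocol and SAP*

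**What the plan says.** All of this is in the combined protocol and SAP.

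- **Analysis.** The sentence that describes the two cohorts begins "The cohort of patients treated with early administration of TXA in the ED" and continues "will be compared to a control group who were not treated with TXA at any point". Both sides are defined by what patients received.
- **Analysis, same paragraph.** Baseline variables are summarised by study group and continuous variables are compared between the study groups. Baseline testing is omitted "because this is a prospective, randomized trial, no formal between-group comparisons of baseline covariates will be performed".
- **Randomization and Blinding.** The study groups are formed by randomisation, TXA or placebo, and the treating teams are blinded.
- **Sample Size.** The calculation contrasts the control group with the treatment group, and "thus the target sample size will be 78 patients per group, 156 in total".
- **Initial Patient Encounter.** Study drug starts in the emergency department as a bolus followed by an 8-hour infusion. "Neither group will receive perioperative bolus dosing of TXA".

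No section mentions intention-to-treat, as-randomised, per-protocol or as-treated analysis, or defines an analysis set. None says how to handle a randomised patient who receives no study drug, only part of it, or TXA later.

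**The concern.** Whether a patient was dosed in the emergency department, and whether that patient got TXA at any later point, are both settled after randomisation. A comparison that sorts patients on them gives up the protection that the plan itself relies on when it omits baseline tests.

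An undosed TXA-arm patient does not fit the treated cohort. A placebo patient given TXA later does not fit the control cohort. If bleeding or frailty influences either event, it also influences transfusion, and losing those patients can bias the primary comparison. The same patients would be lost from the six-month comparisons of VTE, MI, CVA, wound complications and death.

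Such departures are possible here. Dosing is spread over about 8 hours. The Background section says TXA is routine at this institution for elective hip and knee replacement and major spinal procedures. The bar on perioperative bolus dosing and the blinding limit later TXA but do not exclude it.

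**Working it through.** **The plan's own figure.** Inputs from Sample Size: 50% versus 25%, two-sided α = 0.05, 80% power.

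n = [1.96·√(2 × 0.375 × 0.625) + 0.8416·√(0.5 × 0.5 + 0.25 × 0.75)]² / 0.25² = (1.342 + 0.557)² / 0.0625 ≈ 57.7, so 58 per group.

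This matches the plan (power 80.2% by the same approximation). The target of 78 per group is taken as given below; how it follows from 58 is a separate matter.

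**Illustration: inputs.**
- From the documents: 78 per group, a 50% transfusion rate, a chi-square test and two-sided 0.05.
- Assumed, because the documents give no figures: k undosed patients in the TXA arm (2, 4 or 8 of 78, about 3%, 5% or 10%) and their transfusion risk r (30% to 90%).

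**Method.** There is no true effect, so each arm as assigned is at 50%. The dosed TXA-arm patients then have rate q = (0.5 × 78 − k·r)/(78 − k). Rejection probabilities come from exact enumeration of the two binomial counts, using the uncorrected chi-square test. As assigned, the type I error is 4.5%.

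**Undosed TXA-arm patients dropped.** Worked case, k = 8:
- r = 0.7: q = (39 − 5.6)/70 = 47.7%, a spurious gap of 2.3 points
- r = 0.9: q = (39 − 7.2)/70 = 45.4%, a spurious gap of 4.6 points

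| Dropped from TXA arm | Type I error, r = 70% | r = 90% |
|---|---|---|
| 2 | 4.7% | 4.8% |
| 4 | 5.0% | 5.6% |
| 8 | 5.9% | 8.6% |

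For k = 8, the share of rejections favouring TXA is 4.6 of the 5.9 points at r = 70%, and 8.0 of the 8.6 at r = 90%.

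**Direction.** At r = 50% the result is 4.6% to 5.0%, essentially no bias. At r = 30% with k = 8, q = (39 − 2.4)/70 = 52.3%. Type I error is again 5.9%, but 4.6 points of it now favour placebo.

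**Placebo patients dropped for later TXA.** With 8 of 78 dropped at 70% to 90% risk, type I error is 5.9% to 8.6%, mostly favouring placebo. Power against a 25% TXA rate is 83% to 75%, instead of 90.9%.

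**Undosed TXA-arm patients counted as controls (less plausible).** With k = 8 and r = 0.9, the control rate becomes (39 + 7.2)/86 = 53.7% against 45.4%, a gap of 8.3 points. Over r = 70% to 90%, type I error is 8.2% to 17.7%.

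**Cost of analysing as assigned.** If 10% of the TXA arm is undosed and transfused at 50%, that arm's rate is 0.9 × 25% + 0.1 × 50% = 27.5%. Power at 78 per group is 83.4%, against 90.9% with none undosed. At 66 per group (78 × 0.85 = 66.3) it is 76.6%, against 85.6%.

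**The case against.** The strongest reply is that the sentence merely describes the two arms. Controls get placebo and neither group gets perioperative bolus TXA, so never receiving TXA is simply what the control arm is. The Sample Size section describes another randomised trial's control arm in the same way: "there was a transfusion rate of 84.6% in the control group, who never received" TXA. Nor is this the only sentence that names a comparison. The t-test sentence compares the study groups, and the power calculation contrasts the control and treatment groups; Randomization and Blinding defines these terms by randomisation.

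Most of this stands. A reader might infer that the plan commits to an as-treated analysis; the documents do not support that, and an as-randomised intent is likely. A reader might also infer that undosed TXA-arm patients would be counted as controls. That would mean ignoring the definition of control as placebo, so exclusion is the more plausible literal misuse.

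What does not stand is that the matter is therefore settled. The t-test sentence covers continuous variables, not the binary primary outcome. Naming study groups does not say that patients stay in them whatever they received. The receipt wording, with its condition covering the whole course, pulls the other way, and an analyst could follow it without breaching the plan.

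It is also fair to object that the rates of non-receipt are speculative and that only a few patients may be affected. With 2 to 4 patients dropped, the inflation is about one percentage point or less.

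**Conclusion.** The concern holds as a conflict of wording plus a missing statement. The only description of the compared patients is by receipt, the surrounding text points to comparison as randomised, and nothing resolves the two in favour of assignment.

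The likely size is small to moderate. In the exclusion case it runs from almost nothing (2 patients) to a type I error of 8.6% (8 patients at 90% risk), against 4.5% as assigned. The 8.2% to 17.7% range belongs to the less plausible reclassification and should not be taken as the expected harm.

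Every figure rests on assumed non-receipt counts and assumed risks. The direction depends both on which arm loses patients and on whether those patients are at above- or below-average risk of transfusion. The change is worth making because it is cheap and settles the primary comparison before results are seen.

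**What to change.** Replace the sentence in Analysis with:

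*All randomised patients will be analysed in the group to which they were assigned (TXA or placebo), regardless of study drug received or any later TXA.*

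Do not add a per-protocol analysis unless its population is defined; an undefined set would create a second ambiguity.

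Reconcile separately how randomised patients who are never operated on are handled. The Inclusion criteria require surgical treatment, yet study drug starts before surgery. Under Clinical Follow-up "patients will be followed for a period of six months from the day of surgery", and the six-month events under Secondary Outcomes are likewise dated from surgery, so such a patient has no defined start. The replacement sentence also does not settle how missing outcomes among withdrawn patients are treated.

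The cost is one sentence, with no change to the stated sample size, data collection or care. The statistical downside is the dilution shown above: about 83% power instead of 90.9% at 78 per group if 10% of the TXA arm is undosed and transfused at the control rate.

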### Operative Course

Prior to surgery, patients will undergo pre-anesthesia medical clearance and stabilization in coordination with the hospitalist medicine team. Anesthetic type (regional vs. general) will be at the discretion of our anesthesia colleagues.

During surgery, crystalloid maintenance fluids will be administered at a rate of 1.5 cc/kg/hour. Blood losses will be replaced with crystalloid solution in a 3:1 ratio, 5% albumin in a 1:1 ratio, or a combination. Changes of 20% in baseline heart rate or blood pressure which are felt to be due to hypovolemia will be managed with boluses of 10 cc/kg crystalloid solution or 500 cc of 5% albumin. Intraoperative transfusions will be given for hemoglobin levels less than 8 g/dL. If transfused, one unit of packed red blood cells will be administered at a time, with reassessment after each unit. Transfusion triggers will not apply to patients with active myocardial ischemia or hemorrhagic shock.

Surgical management will include either sliding hip screw or cephalomedullary nailing as clinically indicated, performed in routine fashion. Hemostasis will be attained prior to wound closure.

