### Hospital Course

While admitted to the hospital, all patients will be co-managed between the orthopedic trauma service and the hospitalist medicine service. Hemoglobin levels will be checked daily through postoperative day three, and as indicated thereafter. Conservative triggers for blood transfusion will be used for all patients.

Transfusion will be considered for all patients with hemoglobin values of less than 8 g/dL with persistent symptoms or history of significant cardiac disease that may render the patient less able to compensate for significant anemia. Blood transfusion will be considered in all patients with hemoglobin less than 7 g/dL, regardless of symptoms. Hemoglobin triggers will not apply to patients with active myocardial ischemia or hemorrhage. When the decision is made to transfuse, one unit of packed red blood cells will be administered at a time, with reassessment after each unit.

All patients will receive standardized DVT prophylaxis including lower extremity sequential compression devices and low-molecular weight heparin, unless medically contraindicated or full therapeutic anticoagulation is required. Postoperative mobilization will begin as soon as clinically indicated.

Each hospital day, patients will be clinically evaluated for signs of symptomatic venous thromboembolic event (VTE), myocardial infarction (MI), cerebrovascular accident (CVA), and wound complications. Diagnostic workup will be performed only in the setting of acute symptoms. There will be no routine or mandatory screening with the exception of daily clinical evaluation by a member of the OTS trauma team as well as the hospitalist medicine team. VTE will be defined as symptomatic deep venous thrombosis diagnosed by duplex ultrasound, or pulmonary embolism diagnosed by contrast spiral chest CT or ventilation-perfusion scan. MI will be diagnosed using electrocardiogram and serial serum cardiac enzymes. CVA will be defined as transient ischemic attack or stroke diagnosed by head CT or MRI. Wound complications will include hematoma formation, dehiscence, and deep or superficial infection.

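### Name one primary analysis of in-hospital transfusion, independent of 6-month follow-up; adjusting it for presenting hemoglobin is a cheap option whose gain depends on an association the documents do not quantify

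*Combined protocol and SAP*

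**What the plan says.** The Primary Outcome section defines the endpoint as "Proportion of patients transfused at least 1 unit of packed red blood cells during hospital admission". It is therefore known at discharge.

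The Analysis section takes adverse events, the primary outcome and the secondary outcomes together and states that they "will be evaluated using chi-square tests and logistic regression (for categorical variables) if complete follow-up is obtained". It continues: "If follow-up varies because of subject withdrawal or lack of response at 6 months, these outcomes will be estimated and evaluated using survivorship methods", with Kaplan-Meier and Cox regression as the examples. It does not say whether chi-square or logistic regression is primary, and it names no covariate for the regression.

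Presenting hemoglobin appears once, in the list that begins "Baseline variables, including fracture type, surgical procedure, presenting hemoglobin, history of coronary artery disease". The variables in that list are to be summarised overall and by group, without formal comparison. The list also contains length of surgery and length and type of anesthesia.

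Transfusion is tied to hemoglobin. Operative Course: "Intraoperative transfusions will be given for hemoglobin levels less than 8 g/dL". Hospital Course: "Blood transfusion will be considered in all patients with hemoglobin less than 7 g/dL, regardless of symptoms", with a further 8 g/dL ward rule that also needs symptoms or cardiac disease.

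Sample Size states that 58 per group "will provide 80% power to detect a difference in the proportion of patients receiving blood transfusion of 50% versus 25"%, and then: "We will assume an attrition rate of at least 15"%, giving a target of 78 per group.

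**The concern.** Two features of the plan leave room for improvement.

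First, the method for the primary outcome is made to depend on something that does not affect it. A patient who cannot be reached at 6 months still has a known transfusion status. On the literal wording, one such patient moves the primary comparison from a difference in proportions to a survival analysis. The primary effect measure (risk difference, odds ratio or hazard ratio) is then not fixed in advance.

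Second, a baseline measurement that may well predict transfusion is already listed but is given no role in the comparison. If it is prognostic, adjusting for it narrows the confidence interval without extra patients. At stake is some precision and a clear statement of the primary result, not the validity of the trial.

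**Working it through.** **1. The plan's own figure.** Inputs from Sample Size: 50% versus 25%, two-sided alpha 0.05, 80% power. With pooled variance and no continuity correction:

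n = [1.96 × √(2 × 0.375 × 0.625) + 0.842 × √(0.5 × 0.5 + 0.25 × 0.75)]² / 0.25² = (1.342 + 0.557)² / 0.0625 ≈ 57.7, so 58 per group.

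Power at 58 is 80.2%. The stated figure reproduces, and the unadjusted chi-square delivers it.

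**2. How often the complete-follow-up condition would hold.** The target is 2 × 78 = 156 patients. If losses are independent at the plan's 15%, the chance that none is lost is 0.85^156 ≈ 1 × 10⁻¹¹. At 2% it is 0.98^156 ≈ 0.04. Taken literally, the survival route would almost always apply. This shows how often the clause is triggered, not how much harm it does.

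**3. What adjustment would gain.** The documents give neither the SD of presenting hemoglobin nor its association with transfusion. *Assumption:* odds ratio (OR) per SD of 1, 1.5, 2 or 3 (in the direction of lower hemoglobin, more transfusion), normal covariate, marginal risks held at 50% and 25%.

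Trials were simulated under each assumption (40,000 per setting). Two analyses were compared:
- the unadjusted chi-square;
- logistic regression on treatment and the covariate, averaged over all patients to a risk difference (mean predicted risk if all treated, minus mean predicted risk if all on control), with a robust standard error using leverage-corrected residuals r/(1 − h).

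| Assumed OR per SD | 1 | 1.5 | 2 | 3 |
|---|---|---|---|---|
| Power, 78 per group (unadjusted about 91%) | 90% | 91% | 93% | 95% |
| Power, 66 per group (unadjusted about 86%) | 85% | 86% | 88% | 91% |
| Power, 58 per group (unadjusted about 80%) | 80% | 82% | 84% | 88% |
| 95% CI half-width, 58 per group (unadjusted 17.2 points) | 17.2 | 17.0 | 16.5 | 15.6 |
| Change in CI width | 0.5% wider | 1.2% narrower | 4.0% narrower | 8.9% narrower |

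The 66 is 78 × 0.85 = 66.3. Repeat simulations agreed to within about one point of power.

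**4. Type I error.** For the adjusted test it was 4.9 to 5.3% with the small-sample correction and 5.3 to 5.8% without. For chi-square it was 4.5 to 5.3%.

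**5. What the assumed odds ratios mean.** Suppose transfusion occurs when presenting hemoglobin minus the later fall crosses a fixed trigger. Then OR 1.5, 2 and 3 correspond to a presenting-hemoglobin SD of about 0.25, 0.4 and 0.65 times the SD of everything else that decides transfusion. This restates the assumption in familiar units and is not evidence for any one value.

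**The case against.** The strongest reply is that an unadjusted comparison in a randomized trial is standard, that the plan contradicts nothing by using it, and that the benefit of adjustment rests on a number found nowhere in the documents. The protocol also gives reasons for a weaker link: ward transfusion is only to be considered, the 8 g/dL ward rule needs symptoms or cardiac disease, the triggers lapse in active ischemia or hemorrhage, and bleeding continues after presentation. All of this stands, and it is why the gain is stated conditionally. It also stands that the gain is smaller at the planned size. The 58-per-group row would apply only if 1 − 58/78, about 26%, had no primary outcome, which is unlikely for an in-hospital endpoint.

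The authors probably meant the survival route for the 6-month outcomes only, since its trigger is missing response at 6 months. That is likely, but the sentence includes the primary outcome, and one clause would settle it.

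A reader might infer three stronger points that the documents do not support:
- **That the planned test is wrong or underpowered.** It is neither; step 1 reproduces the stated power.
- **That the survival switch would damage the primary result.** With no censoring before discharge, Kaplan-Meier gives the crude proportion. A log-rank test, with first transfusion assumed uniform over four days, kept 79.3 to 79.7% power at 58 per group.
- **That naming two tests inflates the error rate.** Logistic regression on treatment alone, the plain reading, is nearly the same test as chi-square. Claiming whichever of chi-square and a hemoglobin-adjusted test is significant would give about 5.4% at OR 1 and 7.2% at OR 3, but nothing in the plan says the team would do that.

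**Conclusion.** The point holds as a low-cost improvement to consider. Two parts differ in certainty.

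That the plan should name one primary analysis and effect measure for in-hospital transfusion, independent of 6-month response, follows from the text alone.

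That the analysis should adjust for presenting hemoglobin depends on an unquantified association. At 78 per group the change in power ranges from a loss of about half a point (OR 1) to a gain of about 4 points (OR 3), with little change at OR 1.5. Interval width ranges from about 0.5% wider to about 9% narrower. These figures assume a linear effect on the log-odds scale, the plan's 50% and 25% risks, and a hemoglobin value available before dosing for nearly everyone. If the team prefers the unadjusted chi-square as primary, that is valid and need only be stated.

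**What to change.** Before unblinding, amend the Analysis section as follows:

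- **Primary analysis.** One analysis of in-hospital transfusion, applied whatever the 6-month follow-up: logistic regression on treatment and continuous presenting hemoglobin, reported as a standardised risk difference with a robust 95% CI using a small-sample correction (for example leverage-corrected residuals).
- **Covariate definition.** Presenting hemoglobin is the last value drawn before study drug. Initial Patient Encounter mentions no blood draw, so confirm that draw times allow this.
- **Missing values.** Keep patients without a value in the analysis by simple imputation that ignores treatment arm, for example the overall mean.
- **Other covariates.** None that arise after dosing, such as length of surgery or of anesthesia.
- **Supportive analysis.** Unadjusted chi-square.
- **Survival methods.** Limit Kaplan-Meier and Cox to the 6-month outcomes.

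The cost is SAP wording, a check of draw times and a little more analysis work. Sample size and trial conduct do not change. The downside is a CI about 0.5 to 1% wider if hemoglobin is not prognostic, and a slightly liberal test if the small-sample correction is left out.

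### Logistic or Cox regression is planned for VTE, MI and CVA with no provision for an arm without events, where the ordinary ratio is not finite and its usual tests misbehave

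*Combined protocol and SAP*

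**What the plan says.** The Analysis section treats adverse events together with the primary and secondary outcomes. If follow-up is complete, they are evaluated with "chi-square tests and logistic regression (for categorical variables"). If follow-up varies through withdrawal or non-response at six months, "these outcomes will be estimated and evaluated using survivorship methods such as Kaplan-Meier estimation and Cox proportional hazards regression". On reporting it says: "All outcomes will be reported descriptively using appropriate summary statistics, including 95% confidence intervals, where appropriate". Tests are two-sided at 0.05.

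The harm outcomes are narrow. The Secondary Outcomes list has, for example, "Incidence of symptomatic VTE diagnosed within 6 months of surgery", with MI and CVA over the same period.

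The plan names no exact, penalised or other sparse-data method. It does not choose between Wald and likelihood-ratio inference, does not name an interval method, and does not mention a log-rank test. It states no expected rate for VTE, MI or CVA. The Sample Size section sets a target of 78 per group and assumes attrition of at least 15%.

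**The concern.** VTE, MI and CVA are the thrombotic harms of interest for an antifibrinolytic, and several design features point to small counts. Only symptomatic events count, work-up is prompted by acute symptoms alone, and patients with recent events, recurrent or unprovoked VTE, thrombophilia or recent stents are excluded.

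When one arm has no events, the maximum-likelihood odds or hazard ratio does not exist as a finite number. A Wald p-value and interval then carry no information, while a likelihood-ratio p-value can be too small. Two analysts following the plan faithfully could report opposite conclusions from the same table.

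**Working it through.** **The plan's own figure.** For transfusion, 50% v 25%: n = [1.96√(2 × 0.375 × 0.625) + 0.842√(0.5 × 0.5 + 0.25 × 0.75)]² / 0.25² = 57.7, so 58. This agrees with "A sample of 58 subjects per study group (116 in total) will provide 80% power to detect a difference". It concerns transfusion only; there is no corresponding figure for the harm outcomes. The stated target of 78 per arm is used below.

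**Assumption.** Event rates of 1, 2, 3 and 5%, equal in both arms, with 8% added to show where the problem ends. These are not from the documents.

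**Step 1: chance of a zero-event arm.** The chance that one given arm has no events is q = (1 − p)^78, which is 0.457, 0.207, 0.093, 0.018 and 0.0015. The chance that exactly one arm is empty is 2q(1 − q): 50, 33, 17, 4 and 0.3%.

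**Step 2: what the tests do in such a table.** With a and b events, the log odds ratio is log[a(78 − b) / (b(78 − a))] and its variance is 1/a + 1/b + 1/(78 − a) + 1/(78 − b). At a = 0 both are infinite. For 0 v 5:
- Pearson: (5/78)² / [(5/156)(151/156)(2/78)] = 5.17, p = 0.023.
- Likelihood ratio: p = 0.008.
- Logistic Wald: one fit gave a standard error near 15,000 and p = 0.999; another stopped with a singular matrix.
- Cox Wald: log hazard ratio 26, standard error about 212,000, p = 0.9999.

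In the other direction, 0 v 3 gives likelihood-ratio p = 0.040, but Pearson p = 0.080 and Fisher p = 0.245.

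**Step 3: type I error at nominal 5%.** Full enumeration of two binomials, 78 per arm; a zero-event arm counts as non-rejection for Wald. All entries are percentages.

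| Rate | Pearson | Wald | LR, all tables | LR, part from zero-event-arm tables | LR, given events in both arms |
|---|---|---|---|---|---|
| 1 | 0.7 | 0.0 | 4.0 | 4.0 | 0.03 |
| 2 | 3.0 | 0.0 | 8.8 | 8.5 | 0.5 |
| 3 | 4.4 | 0.1 | 9.2 | 7.7 | 1.8 |
| 5 | 4.9 | 1.2 | 7.2 | 2.8 | 4.6 |
| 8 | 5.3 | 3.1 | 5.7 | 0.3 | 5.4 |

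Example for the fifth column at 2%: both arms have events with probability (1 − 0.207)² = 0.629, and 0.629 × 0.52% = 0.3%, which leaves 8.8 − 0.3 = 8.5.

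**Step 4: the Cox route.** Simulation (20,000 runs, 78 per arm, equal follow-up of survivors) at 1, 2, 3 and 5% gave Wald 0.0, 0.0, 0.1, 1.2%; likelihood ratio 3.8, 8.8, 8.9, 7.0%; score (log-rank) 0.8, 2.9, 4.2, 4.4%. Moving to Cox does not remove the problem; the log-rank test does control error.

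**Step 5: effect of attrition.** 78 × 0.85 = 66. With 66 contributing per arm, 2q(1 − q) with q = (1 − p)^66 is 50, 39, 23 and 7%.

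**Step 6: do the alternatives work?** The Miettinen-Nurminen 95% interval for 0 v 5 is 1.5 to 14.2 percentage points. At a difference of 0.0154 the constrained rates are 3.23% and 1.69%, the standard error is √[(0.0323 × 0.9677 + 0.0169 × 0.9831)/78 × 156/155] = 0.0249, and (0.0641 − 0.0154)/0.0249 = 1.96. At 0.1418 the constrained rates are 14.18% and 0, the standard error is 0.0396, and the statistic is −1.96. The Firth penalised likelihood-ratio test is always computable, with size 0.1, 0.9, 2.0 and 3.4% at 1, 2, 3 and 5%. For tripled risks (1 v 3, 2 v 6, 3 v 9%), power is 10, 23 and 36% for Pearson and 4, 18 and 32% for Firth.

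**The case against.** The plan names the chi-square test first. It is computable whenever any event occurs, and its size did not exceed 5.3% at any rate tried from 0.5 to 10%. The survivorship list is open-ended and does not exclude log-rank, and the intervals promised for all outcomes could be binomial or score intervals. A standard error of 15,000 is a visible failure that no statistician would report as reassurance. Event rates are assumed, and at 5% an empty arm is uncommon.

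Much of this stands, and it rules out several stronger readings:
- *That the plan has no sound test for these harms.* On complete follow-up it has one.
- *That likelihood-ratio tests are anti-conservative even with events in both arms.* Over 1 to 5% their size given events in both arms is below 5%; the excess comes from zero-event-arm tables. At a 1% rate there is no inflation at all.
- *That Pearson and Wald routinely conflict.* At 2% v 8% their power is 41% and 15%, and they disagree in 27% of trials. About 18 of those 27 points are tables in which the Wald fit has simply failed.
- *That the plan commits to Wald or ordinary likelihood inference.* It leaves this open.
- *That wound complications share the problem.* They are broadly defined, and nothing shows them to be rare.

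The objection does not dispose of the point. Chi-square gives no estimate or interval. It is given no priority over the model named beside it, and it is set aside when follow-up varies. Leaving the form of inference open is what allows the conclusion to turn on a software default.

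**Conclusion.** The concern holds in a limited form. For VTE, MI and CVA, the named regression models have no provision for an arm without events. If true rates are about 1 to 3%, that situation arises in 17 to 50% of trials per outcome at 78 per arm. The ratio is then not finite, Wald inference cannot detect a difference, and likelihood-ratio inference has an overall size of up to about 9%. With events in both arms, Wald is conservative and the likelihood-ratio test is not inflated. The planned Pearson test is sound, but incomplete follow-up, which the plan's own attrition assumption makes likely, moves the analysis away from it.

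The size of the problem depends on event rates the documents do not give: it is small at 5% and negligible at 8%. The low power for these outcomes is a separate limitation that no choice of test removes. The point merits a change of wording before unblinding and does not put the primary analysis in doubt.

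**What to change.** In Analysis, for VTE, MI and CVA only:
- **Complete follow-up:** make the Pearson chi-square the test, and report the risk difference with a Miettinen-Nurminen score 95% interval.
- **Variable follow-up:** make the log-rank (score) test the test, and report Kaplan-Meier six-month risks by arm.
- **If an odds or hazard ratio is wanted on either route:** use Firth-penalised logistic or Cox regression with profile-likelihood intervals in place of ordinary maximum likelihood.

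Leave the primary outcome and wound complications as planned.

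The cost is a few lines of SAP text, with no extra patients or data. The downside is that effects appear as risk differences, or as slightly shrunken ratios, instead of ordinary odds or hazard ratios.
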